6.1.4 Antimalarial-related outcomes

Although the following outcomes need to share the same definition for a cross-country analysis, it is acknowledge that malaria testing strategies are different across countries. In Senegal all febrile children (≥ 60 days) should be tested for malaria. In Kenya febrile children should be tested only in high risk areas (or seasons), or in low risk areas if there is history of travel to a high risk area or when no other obvious cause of fever is detected. This difference will need to be taken into account when reporting these outcomes. Untested febrile children will need to be described more in detail for Kenya.

6.1.4.1 Proportion of febrile children tested for malaria at Day 0

A child will be considered to be febrile if, at Day 0, history of fever was reported by the caregiver before the consultation or temperature was recorded to be above or equal 37.5 C° or fever was recorded elsewhere in the registry (e.g. diagnosis).

A child will be considered tested for malaria if a malaria test was ordered during the consultation and a test result is available (i.e. positive, negative, invalid/indeterminate, reported but handwriting not readable).

Only febrile children will be counted in the denominator.

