Electronic clinical decision support algorithms (CDSAs) provide an electronic step-by-step guide through a clinical consultation for healthcare providers, supporting the integrated disease management approach promoted by WHO. Recent studies of two such tools, based on IMCI and national guidelines, have demonstrated potential for significant improvements in health outcomes and large reductions in unnecessary antimicrobial prescribing.^{29,30} The use of one such tool by healthcare providers in consultations for all acutely unwell children was found to improve cure rate at day 7 (97% compared to 92% in routine care) whilst reducing antibiotic prescriptions from 84% to 15%.²⁹ Another tool, ePOCT, used for children with fever and integrating point of care diagnostic tests, reduced clinical failure rate to 2% (compared to 5% in routine care) and antibiotic prescriptions to 11% (from 95%).³¹

The mechanisms by which CDSAs impact health worker practice may stem from the fact that the electronic algorithms, by design, provide support in decision making for any combination of clinical findings, whereas paper-based IMCI or national guidelines are, by necessity, reductionist.¹⁰ In a mixed-methods exploration of the reasons for non-adherence to IMCI guidelines by health workers, Lange and colleagues described “cognitive overload” as a contributory factor to non-adherence.³² In such circumstances, support to the complex clinical

decision making process with CDSAs can facilitate health workers to provide higher quality care. This is likely to be particularly true in the case of introducing novel technology such as pulse oximetry, which adds an additional level of complexity to the integrated clinical assessment of children.

Implementing pulse oximetry embedded into a CDSA has the potential to improve the detection of children with severe disease and improve the adherence of healthcare providers to evidence-based, integrated disease management guidelines. We hypothesise that these interventions will result in a reduction in adverse health outcomes through better treatment and referral decisions, and an improvement in quality of care through the rational use of essential medicines and improvements in the health worker and caregiver experience.

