7.3.4 Cost and modelled cost-effectiveness study

When all the cost components have been collected, the data will be aggregated or collated in Excel. Once the summary is completed, a cost profile of the programme activities will be derived and after the total costs of the programme have been calculated, the unit costs will then be derived (i.e. total costs divided by the sample size). These profiles are useful in highlighting major cost components (and thus identifying potential areas where improvements in efficiency may have significant impact on costs). For this evaluation, analysis will focus on full costing and incremental costing approach. Total, average and incremental costs per year will be estimated. Costs associated with increasing the oxygen saturation referral threshold will be estimated based on the additional proportion of children meeting referral criteria.

When available, effectiveness data will be combined with the cost data and cost per DALY averted will be estimated. Effectiveness will be modelled using the information on severe outcomes such as mortality, and secondary hospitalization, adjusting as far as possible the level of severity of illness of the child at presentation.

At primary care facilities, these will include measurements (when taken by healthcare providers) such as anthropometry, respiratory rate, temperature and routine investigations where available (e.g. haemoglobin, CRP), and oxygen saturation (post-intervention/in intervention arms). We will also use diagnosis and severity classification recorded by primary care providers.

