3.1.4 Outcomes

This section provides an overview of the outcomes as listed in the protocol.

Primary outcomes

- ξ Proportion of children referred by a primary healthcare provider to a higher level of care at Day 0 consultation
- ξ Proportion of children prescribed an antibiotic at Day 0

Secondary outcomes

- ξ Proportion of children with a severe complication by Day 7
- ξ Proportion of children admitted to hospital within 24 hours of the Day 0 consultation and as a result of a referral (this is a proxy for 'appropriate referral' of children)
- ξ Proportion of children cured at Day 7 follow-up
- ξ Proportion of children who completed referral as reported at Day 7 follow-up

Other outcomes of interest – hypoxaemia (in post-intervention only)

- ξ Proportion of children with severe ($\text{SpO}_2 < 90\%$), moderate ($\text{SpO}_2 90 – 91\%$) and mild ($\text{SpO}_2 92 – 93\%$) hypoxaemia, adjusted for sites at high altitude
- ξ Proportion of children with hypoxaemia (according to differing cut-offs) with severe complication
- ξ Proportion of children with severe hypoxaemia not meeting any other clinical criteria for severe disease
- ξ Proportion of children referred with hypoxaemia who receive oxygen at hospital

Other outcomes of interest – referral and follow-up

- ξ Proportion of children with non-severe disease referred to a higher level of care on Day 0
- ξ Average length of stay (in days) of children admitted to hospital
- ξ Proportion of children attending scheduled follow-up at the same facility by Day 7
- ξ Proportion of children presenting for unscheduled follow-up to any health facility by Day 7

Other outcomes of interest – antimicrobial prescription

- ξ Proportion of children prescribed a diagnosis-appropriate antibiotic
- ξ Proportion of febrile children tested for malaria at Day 0
- ξ Proportion of malaria positive children prescribed an antimalarial
- ξ Proportion of malaria negative children prescribed an antimalarial
- ξ Proportion of untested children prescribed an antimalarial

Other factors for exploratory analyses

- ξ Additional socio-demographic characteristics, urban / rural location, distance from health facility, key household indicators such as maternal age and education
- ξ Main complaint / symptom categories (including cough / difficulty breathing, fever, diarrhoea and other) and time since onset of symptoms
- ξ Alternative hypoxaemia cut-offs
- ξ Health care provider severity classification

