6.2 Analysis Methods

6.2.1 Analytical Methods

For the primary analysis, pre-intervention and post-intervention periods will be defined as follow:

Pre-intervention period: from the date of data collection start to the date healthcare providers left the facilities for training on the intervention

Post-intervention period: from the date healthcare providers returned to the facilities after training and the devices was delivered to the facilities to the end of data collection

As training was staggered for the facilities, the definitions above will be applied at the facility level.

Outcomes will be described for each time period using summary statistics. In particular, counts and percentages will be used for binary variables and reported with one decimal place; mean and standard deviation (SD) or median (IQR) for continuous variables depending on their

distribution. Mean and median will be displayed with one decimal place and SD and IQR will be presented with two decimal places.

The two primary outcomes will be assessed using a random effects logistic regression model with the cluster included as a random effect. If convergence issues arise due to sparse data, clusters may be dropped or combined to higher grouping level (e.g. district).

Results will be reported with odds ratios, risk differences and their associated 95% confidence intervals (CI).

Secondary outcomes and other binary outcomes of interest will be evaluated in the same way.

Other continuous outcomes of interest will be assessed using random effects linear regression model with the cluster included as a random effect. Results will be reported in terms of adjusted mean differences with associated 95% CIs.

Modelling of secondary outcomes will be performed if numbers allow.

Further exploratory analysis, including interrupted time series analysis to assess change over time and data linked between the quasi-experimental pre-post study and the SPA and time-flow studies. These fall outside the scope of this SAP and will be detailed in a separate document.

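### The febrile denominator for malaria testing partly depends on what providers record, so the pre/post tested proportion can shift without any change in testing

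*SAP*

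**What the plan says.** SAP 3.1.4 lists "Proportion of febrile children tested for malaria at Day 0" among the other outcomes of interest. SAP 6.1.4.1 lets a child enter the febrile group by any one of three routes:

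- "history of fever was reported by the caregiver before the consultation";
- "or temperature was recorded to be above or equal 37.5";
- "fever was recorded elsewhere in the registry (e.g. diagnosis".

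It adds that "Only febrile children will be counted in the denominator". SAP section 6 limits the malaria outcomes to children aged 60 days or more.

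SAP 6.2.1 fits a random-effects logistic model comparing the pre- and post-intervention periods, and says "Secondary outcomes and other binary outcomes of interest will be evaluated in the same way". Counts and percentages are also reported for each period. SAP 6.2.2 adjusts all models for a list of covariates that includes clinical presentations, without saying how these are coded. The sensitivity analyses in SAP 6.2.4 concern the primary outcomes and the hospitalisation-related secondary outcomes. None varies the definition of fever.

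**The concern.** Of the three routes, only caregiver history is settled before the provider acts. The other two exist only if the provider measures or writes something, and the intervention is aimed at the consultation itself:

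- Protocol 7.3.4 describes primary care data as "measurements (when taken by healthcare providers) such as anthropometry, respiratory rate, temperature", so temperature is not guaranteed for every child.
- Protocol 3.2 motivates the study by incomplete assessment in routine care, and says that decision algorithms "provide an electronic step-by-step guide through a clinical consultation for healthcare providers".
- Protocol 6.3 has providers use the algorithm for assessment and diagnosis. SAP 3.1.3 adds refresher training on guidelines.
- Protocol Tab. 4 has separate forms for measurements and diagnoses taken from the algorithm. Protocol 7.1.2 places that recording in the post-intervention period only. The SAP does not say whether registry, in the fever definition, includes this source.

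Membership of the denominator may therefore be affected by the intervention. If it is, the odds ratio and risk difference mix a change in who is labelled febrile with a change in how febrile children are managed. The further description of untested febrile children in Kenya, which SAP 6.1.4 asks for, would draw on the same shifting group.

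**Working it through.** The documents give no fever prevalence, testing rate or recording rate for this outcome, so there is no planned figure to reproduce. Every rate below is an assumption, used only to see whether, how far and in which direction the proportion can move while testing behaviour stays fixed.

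**Formula.** Let h be the share of children with caregiver-reported fever and a their testing rate. Let g be the share febrile by provider record only and b their testing rate. Then

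T = (h·a + g·b) / (h + g).

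If h, a and b stay fixed and g goes from g1 to g2,

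change in T = (b − a)·h·(g2 − g1) / [(h + g1)(h + g2)].

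The sign depends on b − a and on whether g rises or falls. The change is zero if b = a or g2 = g1.

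**Temperature route.** Put g = (1 − h)·t·r, where t is the share of the other children with a temperature of 37.5 or more and r is the share with a temperature recorded. Assume h = 50–60%, a = 70–80%, t = 10–20%, b = 20–30%, and r = 40% before and 95% after. Three of the 16 corner combinations:

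| h | a | t | b | g before → after | T before → after | Change (points) | Odds ratio |
|---|---|---|---|---|---|---|---|
| 0.6 | 0.7 | 0.1 | 0.3 | 0.016 → 0.038 | 69.0% → 67.6% | −1.3 | 0.94 |
| 0.5 | 0.8 | 0.2 | 0.3 | 0.040 → 0.095 | 76.3% → 72.0% | −4.3 | 0.80 |
| 0.5 | 0.8 | 0.2 | 0.2 | 0.040 → 0.095 | 75.6% → 70.4% | −5.1 | 0.77 |

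For the last row, T before = (0.5×0.8 + 0.040×0.2)/0.540 = 0.408/0.540, and T after = (0.400 + 0.095×0.2)/0.595 = 0.419/0.595. The first and last rows are the smallest and largest falls over all 16 corners, so the range is 1.3 to 5.1 points.

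**Other directions.**

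- Provider-identified children tested more often (h = 0.5, a = 0.7, t = 0.2, b = 0.9): 0.386/0.540 = 71.5% before and 0.4355/0.595 = 73.2% after, a rise of 1.7 points.
- Tested equally often (b = a = 0.7): 70.0% in both periods.
- Provider-only share falling, for example because notes move to the tablet (h = 0.5, a = 0.7, b = 0.4, g from 5% to 2%): 0.370/0.550 = 67.3% before and 0.358/0.520 = 68.8% after, a rise of 1.6 points.

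The registry-fever route enters through g in the same way. It is not modelled separately, because nothing in the documents suggests its size.

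**Scale.** Assume 60% of children are febrile and 70% of those are tested, at the initially planned 11,730 (Kenya) or 9,180 (Senegal) children per period. The febrile counts are 7,038 and 5,508. Ignoring clustering, 1.96·√(2×0.7×0.3/n) is 1.5 and 1.7 points. Artefacts of the size shown are thus comparable with, or larger than, random error under these assumptions.

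**Caregiver-only denominator.** Setting g = 0 gives T = a in both periods. The recording artefact disappears, provided caregiver reporting of fever is itself stable.

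**The case against.** A reader might infer that the algorithm does change fever recording and that measured testing will therefore fall. The documents do not support either step. None of them says that temperature or fever recording differs between the periods. The figures on incomplete assessment in Protocol 3.2 concern danger signs, history and examination items, and respiratory rate. The remark in Protocol 7.3.4 that measurements are available when taken belongs to the economic methods. Nor is the direction given. A provider who has measured or diagnosed fever has seen a reason to test, and SAP 6.1.4 says all febrile children of 60 days or more in Senegal should be tested. All of this stands, which is why the claim is that the proportion can shift, with unknown sign.

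The covariate for clinical presentations may also absorb part of the shift in the adjusted odds ratio, if it codes caregiver-reported fever. That is possible but unconfirmed, and it would not correct the raw percentages.

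Replacing the definition outright would have a cost. It would hide missed tests among children whose fever was measured but not reported, and SAP 6.1.4 wants one definition shared across countries. That is a good reason to keep the broad definition and add to it.

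Finally, it is not shown that the caregiver fever question stayed unchanged. A footnote in SAP 6.2.4 records that another caregiver item, on referral urgency, was added in Kenya only post-intervention. The restricted analysis therefore rests on an assumption that should be stated.

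**Conclusion.** The point holds in a limited form. Two of the three routes into the denominator depend on provider recording, which the intervention could alter. The outcome is compared before and after, and no planned analysis isolates the effect. The artefact is a fall of 1.3 to 5.1 points under the assumed ranges, where provider-only febrile children are tested less often and temperature recording rises from 40% to 95%. It is zero if those children are tested equally often or their share is stable. It is a rise if they are tested more often while their share grows. Because the sign is unknown, readers could not correct for it from the reported result alone. Neither primary outcome nor any secondary outcome is affected, so this is an inexpensive improvement to an other outcome of interest and not a threat to the main conclusions.

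**What to change.** In SAP 6.1.4.1:

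1. Keep the broad definition of fever. Also fit and report the same pre/post model with the denominator restricted to children whose caregiver reported fever before the consultation.
2. State in advance that, if the two analyses differ, any statement about change in testing rests on the caregiver-reported denominator.
3. Tabulate by period the share of febrile children entering by each route, and the share of all children with a recorded temperature.
4. Use the same record source for temperature and registry fever in both periods, namely the registry without data from the algorithm.

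This follows what SAP 4.2 already does for cough or difficulty breathing and IMCI classification, which are defined once from caregiver report and once from provider diagnosis and used separately. It needs no new data.

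The cost is one extra model and one table. The restricted analysis omits children with measured but unreported fever and assumes stable caregiver reporting. A registry-only source does not prevent registry entries from thinning out if providers write on the tablet instead, but the table in item 3 would show it.

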6.1.4.2 Proportion of malaria positive children prescribed an antimalarial

A malaria test will be considered positive if a malaria test was ordered during the consultation and was recorded as positive. If the test result is invalid/indeterminate, reported but handwriting not readable or not sure/not reported, the test will not be considered positive.

The child will be considered prescribed with an antimalarial if:

- ξ One or more antimalarial drugs were selected from the antimalarial/treatment drop-down list
- ξ Antimalarial drugs were not selected from the antimalarial/treatment drop-down list but antimalarial drugs were listed in the free text field (conditional to feasibility of assessing free text)

Only children with a positive malaria test result will be counted in the denominator.

6.1.4.3 Proportion of malaria negative children prescribed an antimalarial

A malaria test will be considered negative if a malaria test was ordered during the consultation and the result was negative. If the test result is invalid/indeterminate, or handwriting not readable or not sure/not reported, the test will not be considered negative.

Antimalarial drug prescription will be assessed as described in the point above.

Only children with a negative malaria test result will be counted in the denominator.

6.1.4.4 Proportion of untested children prescribed an antimalarial

A child will be considered untested for malaria if, a malaria test was not ordered during the consultation or a malaria test was ordered during the consultation but a test result is not available.

Antimalarial drug prescription will be assessed as described in the point above.

Only children untested for malaria will be counted in the denominator.

6.1.5 Hypoxaemia-related outcomes – in post-intervention only

6.1.5.1 Proportion of children with severe, moderate and mild hypoxaemia, adjusted for sites at high altitude

Hypoxaemic children will be summarised disaggregated by groups based on the following SpO₂ values ranges: SpO₂ < 90%, 90% ≤ SpO₂ < 92% and 92% ≤ SpO₂ < 94%. All children recruited will be in the denominator.

All facilities in Senegal are in low altitude area and therefore no adjustment is required. Only few facilities from one district in Kenya were above 2000m but cut-off for referral was not adjusted and therefore no adjustment will be applied.

6.1.5.2 Proportion of children with hypoxaemia (according to differing cut-offs) with severe complication

Children with severe complication will be summarized disaggregated by groups based on the following SpO₂ values ranges: SpO₂ < 90%, 90% ≤ SpO₂ < 92% and 92% ≤ SpO₂ < 94%, spurious values and missing values. Each SpO₂ group will be the denominator of each proportion.

6.1.5.3 Proportion of children with severe hypoxaemia not meeting any other clinical criteria for severe disease

Children with severe hypoxaemia (according to country's specific cut-off) not meeting any other clinical criteria for severe disease will be counted in the numerator. All children recruited will be in the denominator.

Severe disease will be defined in a separate document.

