Other outcomes of interest – hypoxaemia

- ξ Proportion of children with severe ($\text{SpO}_2 < 90\%$), moderate ($\text{SpO}_2 90 – 91\%$) and mild hypoxaemia ($\text{SpO}_2 92 – 93\%$), adjusted for sites at high altitude
- ξ Proportion of children with hypoxaemia (according to differing cut-offs) with severe complication
- ξ Proportion of children with severe hypoxaemia not meeting any other clinical criteria for severe disease
- ξ Proportion of children referred with hypoxaemia who receive oxygen at hospital

Other outcomes of interest – referral and follow-up

- ξ Proportion of children with non-severe disease referred to a higher level of care on Day 0
- ξ Average length of stay (in days) of children admitted to hospital
- ξ Proportion of children attending scheduled follow-up at the same facility by Day 7
- ξ Proportion of children presenting for unscheduled follow-up to any health facility by Day 7

Other outcomes of interest – antimicrobial prescription

- ξ Proportion of children prescribed a diagnosis-appropriate antibiotic
- ξ Proportion of febrile children tested for malaria at Day 0
- ξ Proportion of malaria positive children prescribed an antimalarial
- ξ Proportion of malaria negative children prescribed an antimalarial
- ξ Proportion of untested children prescribed an antimalarial

Other exploratory analyses:

- ξ Additional sociodemographic characteristics: urban / rural location, distance from health facility, key household indicators such as maternal age and education
- ξ Additional complaint / symptom categories (fever, diarrhoea and other) and time since onset of symptoms
- ξ Alternative hypoxaemia cut-offs
- ξ Healthcare provider severity classification
- ξ Facility and health system factors – type of facility, healthcare provider qualification and previous training

- ξ Time point (pre, early, late) and pilot site data

6.4.2 **Other mixed methods studies**

These studies will mostly be exploratory, particularly the qualitative studies, which seek to understand perceptions, values, attitudes and beliefs. Process evaluation criteria will be evaluated according to the MRC criteria.³⁵

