6 ANALYSIS

Analyses will be performed and reported overall and by country.

Outcomes will be presented separately for young infants (<60 days) and older children (60 days-59 months), the malaria-related outcomes will be presented only on older children.

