6.1.1 General definitions

Day 7 assessment

Day 7 assessment refers to information reported by the caregiver after Day 0 and recorded in Day 7 form. Data collected as part of unscheduled visits are also integrated in these forms. If multiple successful follow-up assessments for the same child are recorded within the Day7 database, the most recent follow-up assessment will be used. To limit potential recall bias, assessments conducted far beyond the expected follow-up time will be dropped, i.e. 30 days from Day 0.

Death

A child will be considered deceased if, from Day 7 assessment, his/her status at the time of follow-up is “deceased”. In case of implausible death date (i.e. prior to enrolment date), death will be assumed to be within 7 days of Day0.

Hospitalisation

A child will be considered hospitalised if, from Day 7 assessment, he/she went to a hospital, was admitted overnight or if his/her status at the time of follow-up is “hospitalised”. In case of implausible hospitalisation date (i.e. prior to enrolment date), hospitalisation will be assumed to be within 7 days but after 24hrs of Day0.

Hospitalisation within 24hrs of Day0

For the purpose of primary analysis, a child will be considered admitted to hospital within 24hrs of Day0 consultation if the date of hospitalisation is the same as Day0 date or is one day after Day0 date.

Referral

A child will be considered to be referred (either to a hospital or to an inpatient part of a larger primary healthcare facility) if, at Day0, the research assistant confirms that an urgent referral advice was recorded for the child. If urgency is unknown, referral will be assumed to be urgent.

Antibiotics

Antibiotics will be defined in accordance with the WHO antibiotic point prevalence survey (PPS) methodology [4, 5, 6] and therefore only antibacterials for systemic use will be taken into account.

SpO2 values

SpO₂ should be recorded during the Day0. For the outcomes, the following measures will be taken for spurious and missing SpO₂ values:

- If SpO₂ value is not available, the child will be assumed normoxaemic
- If $70 \leq \text{SpO}_2 < 90\%$, the child will be assumed (with accuracy) to have severe hypoxaemia
- If $40 \leq \text{SpO}_2 < 70\%$, the child will be assumed (with low accuracy) to have severe hypoxaemia
- If $\text{SpO}_2 < 40\%$, the value will be considered spurious (e.g. due to incorrect dataentry) and treated as not available, i.e. the child will be assumed normoxaemic.

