Additionally, a description of SpO₂ values distribution will be provided based on the following cut-offs:

- $95\% \leq \text{SpO}_2 < 100\%$
- $94\% \leq \text{SpO}_2 < 95\%$
- $92\% \leq \text{SpO}_2 < 94\%$
- $90\% \leq \text{SpO}_2 < 92\%$
- $70\% \leq \text{SpO}_2 < 90\%$ (severe hypoxaemia, accuracy)
- $40\% \leq \text{SpO}_2 < 70\%$ (severe hypoxaemia, but low accuracy)
- Spurious ($0\% \leq \text{SpO}_2 < 40\%$)
- Missing

Mild hypoxaemia

$92\% \leq \text{SpO}_2 < 94\%$ (Kenya)

Moderate hypoxaemia

$90\% \leq \text{SpO}_2 < 92\%$ (Kenya)

$92\% \leq \text{SpO}_2 < 95\%$ (Senegal)

Severe hypoxaemia

$\text{SpO}_2 < 90\%$ (Kenya)

$\text{SpO}_2 < 92\%$ (Senegal)

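### SAP 6.1.5.3 counts severe hypoxaemia below 90% in Kenya but below 92% in Senegal, so its pooled figure has no single definition and does not match the protocol outcome or the prevalence bands in 6.1.5.1

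*SAP*

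**What the plan says.** - **Protocol 6.4.1 and SAP 3.1.4** list the outcome "Proportion of children with severe ($\text{SpO}_2 < 90\%$), moderate" 90–91% and mild 92–93%, with no split by country.
- **SAP 6.1.1, SpO2 values**, gives a handling rule for all children: "If $70 \leq \text{SpO}_2 < 90\%$, the child will be assumed (with accuracy) to have severe hypoxaemia". Readings from 40% to below 70% are also severe, with low accuracy. The distribution rows that follow repeat this without a country split.
- **SAP 6.1.1, hypoxaemia definitions**, then splits by country. For Kenya, severe is below 90%, moderate 90% to below 92%, and mild 92% to below 94%. For Senegal, severe is below 92% and moderate 92% to below 95%, with no mild class.
- **SAP 6.1.5.1 and 6.1.5.2** use below 90%, 90% to below 92%, and 92% to below 94% for both countries.
- **SAP 6.1.5.3** uses the country's "specific cut-off) not meeting any other clinical criteria for severe disease will be counted in the numerator", with all recruited children as the denominator.
- **SAP 6.1.5.4** uses hypoxaemia by the country's cut-off and names no severity level.
- **Pooling:** "Analyses will be performed and reported overall and by country" (SAP 6). SAP 3.7 and protocol 7.3 also plan a pooled cross-country analysis.

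**The concern.** One label carries two meanings within a single results section. The protocol's case for oximetry (3.1) is that it finds children whom clinical signs miss, and 6.1.5.3 is the outcome that measures this. As written, its pooled value is neither the proportion below 90% nor the proportion below 92% without other severe criteria. It cannot be checked against the prevalence rows beside it or against the protocol outcome. SAP 1.1 says the analysis complies with the protocol except where otherwise detailed. The Senegal definition is written out, but it is neither identified nor justified as a departure.

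Protocol 7.3.4 also plans to cost a higher SpO2 referral threshold from the additional children who would meet it. That is easier if the 90–91% group stays separate.

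**Working it through.** This is a question of definitions. The plan states no figure for this outcome, so there is none to reproduce.

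**Step 1. Classify each reading under the competing definitions.**

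| SpO2 (%) | Protocol 6.4.1, SAP 3.1.4, ranges of 6.1.5.1 | SAP 6.1.1 Kenya | SAP 6.1.1 Senegal |
|---|---|---|---|
| 89 | severe | severe | severe |
| 90, 91 | moderate | moderate | **severe** |
| 92, 93 | mild | mild | **moderate** |
| 94 | none | none | **moderate** |
| 95 | none | none | none |

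Kenya agrees throughout. Senegal disagrees at every reading from 90 to 94. Only the 90–91 disagreement enters 6.1.5.3.

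**Step 2. Consequence for the Senegal table.** Let A be the children below 90% with no other severe criteria, C those below 90% with other severe criteria, and B those at 90–91% with no other severe criteria. The 6.1.5.3 numerator is A + B, and the below-90% count in 6.1.5.1 is A + C. The numerator is therefore not a subset of that count, and it exceeds it whenever B > C.

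**Step 3. Consequence for the pooled figure.** Let p be the pooled proportion below 90% with no other severe criteria, b Senegal's proportion at 90–91% with no other severe criteria, and w Senegal's share of recruited children. The denominator is all recruited children, so:

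- common definition: p
- as written: p + w × b

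The excess w × b cannot be negative, whatever the clinical profile of the children at 90–91%.

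**Step 4. Weight.** The initially planned sizes are 11,730 (Kenya) and 9,180 (Senegal), from protocol 6.6.1. So w = 9,180 / (11,730 + 9,180) = 9,180 / 20,910 = 0.439. Both countries later gained two facilities. At unchanged size per facility, w = (20 × 510) / (19 × 690 + 20 × 510) = 10,200 / 23,310 = 0.438, which is practically the same. The revised sizes per facility are not given, and the actual w will come from enrolment.

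**Step 5. Size.** The documents give neither p nor b. The values below are assumptions that show the range. Cells are p + 0.439 × b, with the ratio to p in brackets.

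| p | b = 0.2% | b = 0.5% | b = 1.0% | b = 2.0% |
|---|---|---|---|---|
| 0.2% | 0.29% (1.44) | 0.42% (2.10) | 0.64% (3.20) | 1.08% (5.39) |
| 0.5% | 0.59% (1.18) | 0.72% (1.44) | 0.94% (1.88) | 1.38% (2.76) |
| 1.0% | 1.09% (1.09) | 1.22% (1.22) | 1.44% (1.44) | 1.88% (1.88) |

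**The case against.** The country split looks deliberate. It is set out in 6.1.1, named in 6.1.5.3, and matches the referral cut-offs in protocol 6.3. Results are also given by country, and alternative cut-offs are listed for exploratory work. The outcome is descriptive and secondary to the trial's main question. All of this stands, and it limits the weight of the point. It does not cure the pooled figure: country results do not give that figure a definition, and SAP 3.1.4 places the exploratory work in a separate document. A referral threshold is also a different thing from the protocol's measurement definition of severe.

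A reader might infer more than the documents support:

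- **That the two cut-offs bias a Kenya–Senegal comparison that a common cut-off would make sound.** It would not. SAP 4.2 says oximetry was indicated for all children in Kenya but only for some in Senegal. SAP 6.1.1 counts a missing SpO2 as normoxaemic, and the denominator is all recruited children. Ascertainment differs between countries under any cut-off.
- **That 6.1.5.4 should also move to below 90%.** The protocol outcome there is hypoxaemia, not severe hypoxaemia, and protocol hypoxaemia extends to 93%. The fault in 6.1.5.4 is that the level is not stated. Under 6.1.1 it could mean below 90% and 92%, or below 94% and 95%.
- **That the SpO2 distribution rows distort the hypoxaemia results because the top row stops short of 100%.** A reading of exactly 100% does fall in no row, but no hypoxaemia count changes. It reads as a slip.
- **That dropping the altitude adjustment misstates prevalence.** The outcome title still says "hypoxaemia, adjusted for sites at high altitude", while 6.1.5.1 says "cut-off for referral was not adjusted and therefore no adjustment will be applied". Title and text disagree, but the departure is disclosed. The SAP reports only a few facilities above 2000 m, and protocol 6.3 expects little effect on cut-offs below 2500 m. The county range in protocol 6.1.1 reaches 2700 m, but the documents do not show a study facility above 2500 m.

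**Conclusion.** The inconsistency is certain from the text. Severe hypoxaemia is below 90% for all children in four places, and below 92% for Senegal in the definition that 6.1.5.3 uses. The pooled 6.1.5.3 result therefore mixes two definitions and is higher than the common-definition result by w × b.

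The size is not known. At w of about 0.44, and with a common-definition figure assumed at 0.5% and b at 0.2% to 2.0%, the pooled figure is 1.18 to 2.76 times as large. The ratio is smaller if the common-definition figure is higher and larger if it is lower. No single value in that range has support in the documents. The change is worth making because it alters a reported result at very little cost. It does not bear on the primary outcomes, the sample size or patient management.

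**What to change.** 1. Reconcile SAP 3.1.4, both parts of 6.1.1 (the SpO2 handling rule and the country definitions) and 6.1.5, so that severe has one meaning.
2. In 6.1.5.3, report the pooled result on the protocol's SpO2 below-90% band. Report Senegal's below-92% result separately, within country, labelled 'below the national referral cut-off'.
3. In 6.1.5.4, state which SpO2 level the country cut-off means, and put it in the label of any pooled figure. Do not impose below 90% there.
4. Add a note to the tables that Kenya–Senegal differences also reflect different oximetry indications and the rule that a missing SpO2 counts as normoxaemic.
5. Editorial only: close the top distribution row at 100% inclusive, and align the altitude wording in the outcome title with the text of 6.1.5.1.

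The cost is SAP wording and about one extra table row, with no new data. The downside is two figures for Senegal, which the labels keep apart. These are reporting definitions; no view is taken on the clinical referral cut-offs, which stay as they are.
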